#### 5.4 Baseline characteristics

Participant characteristics will be presented as an overall summary regardless of treatment sequence. Normally and non-normally distributed continuous variables will be summarized as mean  $\pm$  95 % confidence interval (CI) and median (interquartile range (IQR)). Categorical variables will be presented as numbers and percentages.

### **6 Statistical plan**

#### 6.1 Statistical methods

The mean between-treatment ( $\pm 95\%$  CI) change in the primary endpoints of cardiac output (CO) and insulin sensitivity, as well as other single-time-point outcomes, will be analysed using a linear mixed-effects model with fixed effects for treatment and treatment sequence (order) and a random intercept for participant to account for within-participant correlation. Fixed effects will be estimated using a restricted maximum likelihood (REML) procedure and compared using the Kenward–Roger method. Estimated marginal means (EMMs) for treatment will be obtained from the fitted model, and pairwise between-treatment differences will be tested. For log-transformed outcomes, EMMs will be back-transformed to the original scale and reported as geometric means.

Analysis of temporal effects during the acute-on-chronic intervention (repeated-measures data) will be conducted using linear mixed-effects models with fixed effects for treatment, time, and their

interaction, as well as treatment sequence (order), and random intercepts for participant and for visits nested within participants. Fixed effects will be estimated using a restricted maximum likelihood (REML) procedure and compared using the Kenward–Roger method. Estimated marginal means (EMMs) for treatment will be obtained at each time point from the fitted model, and pairwise between-treatment differences will be tested at each time point. For log-transformed outcomes, EMMs will be back-transformed to the original scale.

Assumptions for the statistical analysis will be assessed through inspection of linearity, homoscedasticity, and normality of residuals using plots (residuals vs. fitted values, scale–location plots, and normal Q–Q plots). If violations occur, including significant skewness of residuals or outcome variables, data will be log-transformed and reported accordingly. To enable log transformation, a small constant will be added to all values if multiple observations of 0.0 are present in the dataset. For log-transformed variables, results will be displayed on a logarithmic scale, and between-treatment effects will be expressed as relative changes derived from the model outcomes. If neither the original linear mixed model nor the log-transformed linear mixed model can be applied, data will instead be analysed using McNemar’s exact test, assuming that order and visit have no effect, with a contextual cut-off applied for classification.

Secondary endpoints will be analysed and interpreted independently of the primary endpoint results and without adhering to a hierarchical testing sequence. The analysis methods for the secondary endpoints will mirror those outlined for the primary outcomes. No imputation will be performed for missing data.

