## **2: Study design**

### *2.1 Trial design*

This is a single-center, randomized, double-blind, placebo-controlled crossover study of the effects of 28-day treatment with a novel lactate-ketone ester in healthy middle-aged subjects with obesity.

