### *2.2 Randomization*

Participants are randomized 1:1 to receive either oral LaKe (25 mL, Mmimetika Biosciences, Aarhus, Denmark) x 2 daily or non-caloric placebo drink x 2 daily. Each study period lasts 28 days separated by a 28-day washout period.

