### **3 Cohort size**

Power calculations were conducted independently for each co-primary outcome. The outcomes are analysed and interpreted independently, and the statistical considerations, including power and sample size calculations, are specific to the outcome presented here. Pre-specified co-primary outcomes will be reported regardless of significance in separate analyses and manuscripts without interaction

For the co-primary outcome of insulin sensitivity assessed by a hyperinsulinemic-euglycemic clamp after ingestion of LaKe on the trial day, we aim to detect a relative difference of 30 % (from the mean  $3.0 \text{ mg} \cdot \text{kg}^{-1} \cdot \text{min}^{-1}$  with a standard deviation of  $0.9 \text{ mg} \cdot \text{kg}^{-1} \cdot \text{min}^{-1}$ ), a power of 80 %, and a two-tailed significance level of 5 %. Thus, 10 participants need to be enrolled.

For the co-primary outcome of CO assessed by echocardiographic measurements after ingestion of LaKe on the trial day, we anticipate an increase of CO up to 7.0 liter/min and therefore aim to detect a relative difference of 25 % (from the mean 5.6 liter/min with a standard deviation of 1.4 liter/min), a power of 80 %, and a two-tailed significance level of 5 %. Thus, 10 participants need to be enrolled.

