#### 4.2 Study dropout

The occurrence of any condition necessitating withdrawal from the study, whether due to safety concerns, disease progression, subject choice, or non-adherence to protocol requirements, may serve as a reason for study withdrawal. Participants who withdraw will be replaced to reach the target enrollment as specified in the power analysis. The CONSORT flow diagram will present the timing, numbers, and reasons for withdrawals.

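### The crossover models adjust for treatment sequence but have no period effect, so a shift between the two visits widens the interval or biases the treatment difference

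*SAP*

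**What the plan says.** Section 2.1 describes a "single-center, randomized, double-blind, placebo-controlled crossover study", and section 2.2 adds that "Each study period lasts 28 days separated by a 28-day washout period". Single-time-point outcomes, including cardiac output and insulin sensitivity, are analysed under section 6.1 with a "linear mixed-effects model with fixed effects for treatment and treatment sequence (order) and a random intercept for participant".

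The repeated-measures model has treatment, time and their interaction, "as well as treatment sequence (order), and random intercepts for participant and for visits nested within participants". Time there is time within the trial day, not study period.

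If neither the linear nor the log-transformed model can be used, the fallback is McNemar's exact test, "assuming that order and visit have no effect". Section 6.1 goes on to apply the primary methods to the secondary endpoints.

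Section 5.2 leaves participants who do not complete both periods out of the final analysis. Under section 4.2, "Participants who withdraw will be replaced to reach the target enrollment as specified in the power analysis".

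**The concern.** Treatment is compared within participants, and sequence differs only between participants. A sequence term therefore cannot protect the treatment contrast from anything that changes systematically between the first and second endpoint visits. That is the job of a period term, and the plan has none. It appears to adjust for the crossover layout but in practice does not.

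An unmodelled period shift goes into the scatter of the paired differences, which widens the interval and costs power. If the analysed sequences are unequal in size, part of the shift also goes into the treatment estimate. With only 10 participants, and with non-completers excluded and replaced, a 5:5 split among those analysed is not assured.

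**Working it through.** **Inputs.** Section 3 gives N = 10, a two-sided 5% level and 80% power. The target for insulin sensitivity is 30% of 3.0 = 0.9 mg/kg/min with SD 0.9. For cardiac output it is 25% of 5.6 = 1.4 L/min with SD 1.4. Effect/SD is therefore 1 for both. The period shift *p* is not in the SAP; values from 0 to 1 SD are assumed.

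**Reproducing N.** Section 3 does not say which SD is meant. Take it as the SD of the paired differences (the same as a within-participant correlation of 0.5 if it is a between-participant SD). A paired t-test with N = 10, 9 df and noncentrality √10 × 1 = 3.16 has power 80.3%. The planned N reproduces.

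**What each model estimates.** Let *D* be LaKe minus placebo within a participant and τ the treatment effect. Participant and sequence effects cancel in *D*, which leaves:

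- placebo first (n1 participants): E(*D*) = τ + *p*
- LaKe first (n2 participants): E(*D*) = τ − *p*

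Without period, the estimate is the mean of all *D*, with expectation τ + *p*(n1 − n2)/N. With period, it is the average of the two sequence-specific means, with expectation τ.

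REML fits to one simulated 6:4 data set confirm this. Treatment plus sequence gave 1.0539 (SE 0.2899), equal to the plain mean of the paired differences and its SE. Adding period gave 0.9238 (SE 0.2135), equal to the average of the two sequence means.

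**Interval width.** In SD units, the expected variance of *D* without period is 1 + *p*²[1 − ((n1 − n2)/N)²] × N/(N − 1). At 5:5 and *p* = 0.5 this is 1 + 0.25 × 10/9 = 1.278, so the half-width is 2.262 × √(1.278/10) = 0.81. With period it is 2.306 × √[0.25(1/5 + 1/5)] = 0.73.

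**Power and error.** From 200,000 simulated trials per scenario, with a true effect of 1 SD for power and 0 for type I error:

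| Split | Shift (SD) | Bias without period (SD) | Half-width without / with | Rejection at true effect, without / with | Type I error without |
|---|---|---|---|---|---|
| 5:5 | 0 | 0 | 0.715 / 0.729 | 80.3% / 79.0% | 4.92% |
| 5:5 | 0.25 | 0 | 0.740 / 0.729 | 78.3% / 79.0% | 4.37% |
| 5:5 | 0.5 | 0 | 0.809 / 0.729 | 72.0% / 79.0% | 3.05% |
| 5:5 | 1.0 | 0 | 1.039 / 0.729 | 48.2% / 79.0% | 0.64% |
| 6:4 | 0 | 0 | 0.715 / 0.744 | 80.2% / 77.3% | 4.93% |
| 6:4 | 0.5 | 0.10 | 0.805 / 0.744 | 80.7% / 77.5% | 3.76% |
| 6:4 | 1.0 | 0.20 | 1.028 / 0.744 | 69.5% / 77.4% | 1.65% |
| 7:3 | 0 | 0 | 0.715 / 0.796 | 80.3% / 72.0% | 5.01% |
| 7:3 | 0.5 | 0.20 | 0.794 / 0.796 | 87.8% / 71.7% | 6.00% |
| 7:3 | 1.0 | 0.40 | 0.995 / 0.796 | 87.0% / 71.7% | 6.31% |

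With the period term, bias is zero and type I error is about 5% in every row. In the unbalanced rows the shift was set to favour LaKe, so the high rejection rates without period include bias and are not a gain in power.

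**In outcome units, at a shift of 0.5 SD.** At 6:4 the bias is 0.10 × 1.4 = 0.14 L/min and 0.10 × 0.9 = 0.09 mg/kg/min. At 7:3 it is 0.20 × 1.4 = 0.28 L/min and 0.20 × 0.9 = 0.18 mg/kg/min.

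**How easily imbalance arises.** As an illustration, suppose 12 are randomised 6:6 and two drop out at random. Both come from the same sequence, leaving 6:4, with probability 2 × 15/66 = 45%.

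**The case against.** - **Order might mean first or second visit.** If it is coded that way, the term is the period effect. The fallback sentence does not fully settle this, because its mention of visit could refer to the random visit intercept. But the plan calls the term treatment sequence and names order and visit separately, so a programmer following the text would code the sequence group. If period was meant, the wording still has to change.
- **The repeated-measures model contains visit.** It does, as a random intercept. That absorbs visit-level scatter but does not estimate or remove a systematic shift from the first visit to the second.
- **The bias is conditional on the imbalance that occurs.** This stands. Averaged over simple 1:1 randomisation, the estimate without period is unbiased, and simulated type I error was 5.0% to 5.2% for shifts of 0.25 to 1 SD. The trial will nevertheless be analysed with one particular split, and its estimate carries that split's bias.
- **The shifts are assumed, and the largest is extreme.** This also stands. A 1.0 SD shift equals the whole planned treatment effect. At 0.25 SD and 5:5 the loss is under 1 point. Blocking, and the sequence given to replacements, may be set in the protocol, so 7:3 is only illustrative.
- **Complete pairs are not certain.** Section 5.2 also speaks of analysing all collected data, and a completer may lack one outcome. The sequence term is then not exactly inert, but it still does not model period.

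**Conclusion.** The point holds: section 6.1 is wrong as written. The single-time-point model's only crossover adjustment does nothing for the treatment contrast on complete pairs, and neither model removes a systematic period shift.

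The size of the harm depends on a shift the SAP does not give. In a balanced trial it is negligible below about 0.2 SD. At 0.5 SD it is 7 points of power and an interval about 11% wider than with the period term; at 1.0 SD, 31 points and about 43%. In an unbalanced trial there is also bias of *p*(n1 − n2)/N, and at 7:3 type I error is about 6%. These figures take the SD in section 3 as the SD of paired differences and assume complete pairs.

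Because the shift cannot be known in advance, the protection has to be pre-specified. Adding it after seeing the data would be a post-hoc choice.

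**What to change.** In section 6.1, add period (first or second study period) as a fixed effect to both models:

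- single-time-point outcomes: treatment + period + sequence, with a random participant intercept
- repeated measures: treatment × time + period + sequence, with random intercepts for participant and for visit within participant

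Keep REML and Kenward–Roger. Sequence may stay, but not as the only crossover adjustment. State how sequence and period are coded, and drop the ambiguous word *order*.

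The cost is one line of text and one degree of freedom. With no period shift, power at N = 10 falls from about 80% to 79% at 5:5, 77% at 6:4 and 72% at 7:3. The larger loss under imbalance is the price of an estimate free of period bias. Design and data collection do not change.

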### *2.3 Endpoints*

**Primary:** The study has two co-primary endpoints:

- 1) Between-treatment difference in cardiac output during acute-on-chronic intervention
- 2) Between-treatment difference in insulin sensitivity during acute-on-chronic intervention

**Secondary:** Between-treatment difference in:

- 1) Safety and tolerability: 10-item Beverage tolerability Questionnaire (BTQ)

- 2) Other echocardiographic parameters: Left ventricular ejection fraction, global longitudinal strain, left ventricular end-diastolic volume, left ventricular end-systolic volume, tricuspid annular plane systolic excursion, mitral inflow velocities (E and A), mitral plane velocities in the lateral mitral annulus (e' and s'), global work index (GWI)
- 3) Lipolysis
- 4) Body composition
- 5) Hormones and metabolites

**Exploratory:** Between-treatment difference in:

- 1) Lactate and BHB concentrations
- 2) Acid-base status
- 3) Biochemic 'safety': concentration measurements of CRP, sodium, potassium, leukocytes, thrombocytes
- 4) Validated questionnaires on appetite and mental well-being

**Timing of endpoints:** The primary and secondary endpoints are measured at each study visit following the 28-day treatment period.

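### Section 6.1 requires a log transformation for any model violation, whatever the direction of skew, and has no rule for keeping the original scale when logging fits worse (minor)

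*SAP*

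**What the plan says.** Section 6.1 names the checks: "Assumptions for the statistical analysis will be assessed through inspection of linearity, homoscedasticity, and normality of residuals using plots". The consequence follows directly: "If violations occur, including significant skewness of residuals or outcome variables, data will be log-transformed and reported accordingly". The instruction is mandatory, covers every kind of violation, and makes no distinction between right and left skew or between rising and falling spread. No other remedy is offered at this step.

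Two sentences surround it. For zeros, "a small constant will be added to all values if multiple observations of 0.0 are present in the dataset". As a last resort, "If neither the original linear mixed model nor the log-transformed linear mixed model can be applied, data will instead be analysed using McNemar’s exact test", with a cut-off left to context. The SAP does not say that the log model is compared with the original, that the original stands if it fits better, or what makes a model impossible to apply.

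The rule reaches beyond the two co-primary endpoints: "The analysis methods for the secondary endpoints will mirror those outlined for the primary outcomes". Section 2.3 lists secondary outcomes of quite different kinds, among them "Left ventricular ejection fraction, global longitudinal strain, left ventricular end-diastolic volume", and exploratory ones such as "Validated questionnaires on appetite and mental well-being". The exploratory outcomes are not named in the sentence on secondary endpoints, but those measured once per visit fall under the single-time-point outcomes of Section 6.1.

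**The concern.** A logarithm compresses the upper tail and stretches the lower one. It repairs right skew and spread that grows with the mean. It aggravates left skew and spread that shrinks with the mean. A rule that applies it to all of these will sometimes move the analysis to a scale that fits worse than the one it left.

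Outcomes with an upper bound or a ceiling, such as ejection fraction or a well-being score in healthy people, could be left-skewed. An analyst who follows the text would then report a less efficient test as a relative change, although the untransformed analysis needed no repair. If the log model is judged unusable as well, the text leads to a dichotomised comparison in about 10 participants.

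**Working it through.** **The plan's own figure.** The rule rests on no stated number, but the sample size fixes the setting. In Section 3, for insulin sensitivity, "we aim to detect a relative difference of 30"% of 3.0 is 0.9, with SD 0.9. For cardiac output, 25% of 5.6 is 1.4, with SD 1.4. Both give difference/SD = 1.0. If the SD is taken as that of the within-person difference, a paired t-test with n = 10 has noncentrality 1.0 × √10 = 3.16 on 9 degrees of freedom. Power is 0.803 (0.748 at n = 9), so the stated 10 is reproduced.

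**Why direction matters.** Write g for skewness and κ for kurtosis (normal = 3). To first order in the CV:

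skewness after log ≈ g − 1.5 × CV × (κ − g² − 1)

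Since κ is at least g² + 1, the shift is never upward. A gamma-shaped outcome with |g| = 1 has κ = 4.5, so the shift is −1.5 × CV × 2.5 = −3.75 × CV. At CV 10% (assumed mean 60, SD 6) this predicts −1.00 − 0.375 = −1.38 under left skew and 1.00 − 0.375 = 0.63 under right skew. Simulation gave −1.00 to −1.53, and 0.99 to 0.67. At the planning values (positive values only), left skew went from −0.85 to −3.55 for cardiac output and from −0.74 to −3.42 for insulin sensitivity. Right skew went from 1.00 to 0.30 and from 1.00 to 0.18.

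**Variance.** SD(log y) ≈ SD(y)/mean. With a constant SD of 1.4, the means of 5.6 and 7.0 in Section 3 give 0.25 and 0.20 on the log scale, so equal spread becomes unequal. If SD falls as the mean rises, the imbalance grows.

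**Cost in power.** Assumptions, none from the SAP except n = 10 and the 25% CV (1.4/5.6): gamma errors with skewness −1.0, intraclass correlation 0.5, true difference equal to the SD of the paired difference, paired t-test, 40,000 trials. At CV 25%, the 0.8% of trials with a non-positive value were dropped from the run in which every trial was logged. The last column is a separate run in which a 5% skewness test on the residuals stands in for plot inspection.

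| CV | Residual skewness after log | Power raw → log, every trial logged | Power raw → rule, only flagged trials logged |
|---|---|---|---|
| 8% | −1.26 | 80.3% → 78.7% (loss 1.6) | 80.4% → 79.8% (loss 0.6) |
| 15% | −1.57 | 80.4% → 76.9% (loss 3.5) | 80.5% → 79.3% (loss 1.2) |
| 25% | −2.53 | 80.5% → 73.2% (loss 7.3) | 80.7% → 78.3% (loss 2.4) |

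The screen flags about 9% of trials, because with two observations per person the fitted residuals show a median skewness of only about −0.27. Within flagged trials, power fell from 69% to 63% at CV 8% and from 68% to 40% at CV 25%. A second run, flagging 7% to 8%, gave 72% raw against 65%, 60% and 48% on the log scale at the three CVs. In that run, skewness was worse after logging in over 99% of flagged trials.

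**Type I error and the opposite case.** At the planning values with left-skewed errors, type I error was 0.048 raw against 0.041 (cardiac output) and 0.039 (insulin sensitivity) after logging, so there is no inflation. With right skew of the same size, logging raised power from 0.806 and 0.802 to 0.832 in both.

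**The next step.** Exact McNemar needs at least six discordant pairs, all in one direction, to reach P < 0.05 (2 × 0.5⁶ = 0.031; five give 0.0625). With an assumed pooled-median cut-off, its power in the same setting was about 26% to 28%, against about 81% for the raw paired test.

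**The case against.** The strongest reply is that the harm is hypothetical. The SAP names no outcome as left-skewed, and for positive, right-skewed measurements the rule does what it should. The plots would rarely trigger it at this sample size, and an experienced analyst would see that the log scale looks worse. Section 6.1 also foresees that the log model may fail, so a poor log result need not be the one reported. All of this stands, and it is why the point is minor. It does not remove the defect: the text mandates the log, sets no comparison with the original, and sends a double failure to a far weaker test.

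Several stronger readings are tempting and unsupported:

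- **That the rule degrades the analysis in general.** It does so only for left skew or falling spread.
- **That cardiac output stands to lose 7 points.** That figure borrows its CV and assumes left skew in every trial, every one logged. Nothing in the SAP says cardiac output is left-skewed.
- **That acid-base status is a clear example because pH is already a logarithm.** The SAP does not mention pH, and at an assumed CV of 0.5% logging changes almost nothing (0.809 against 0.808).
- **That false positives increase.** They do not in these scenarios.

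**Conclusion.** The concern holds as a minor defect in a contingency rule. Section 6.1 prescribes the log without regard to direction and gives no criterion for retaining the original scale. Where residuals are left-skewed, or spread falls with the mean, following it worsens the fit.

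Under the assumed skewness of −1.0, the cost ranges from about half a point of power on average, when only flagged trials are logged at a small CV, to about 7 points when every trial is logged at CV 25%. In the minority of trials actually flagged, it is about 6 to 7 points at CV 8% and 24 to 28 points at CV 25%. The size depends on the assumed skewness, the CV and the residual-skewness screen. The SAP's other trigger, skewness of the outcome variable itself, would fire differently and was not simulated. The loss from spread that falls with the mean was reasoned through and not simulated. The possible push towards McNemar is an added risk whose likelihood cannot be stated, because the SAP does not define when a model cannot be applied.

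**What to change.** Replace the sentence in Section 6.1 with: 'Data will be log-transformed only if residuals are right-skewed or their spread rises with the fitted mean, all values are positive (after any constant added for zeros), and the residual plots improve on the log scale; otherwise the original-scale linear mixed model is retained.'

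The McNemar sentence should then be aligned, so that a failed log transformation does not by itself lead there. A permutation test of within-participant differences may be added for single-time-point outcomes, but it is optional: the original-scale test held its level in the simulations, and such a test does not directly cover the treatment-by-time models.

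The cost is one sentence and a second set of residual plots for affected outcomes. Sample size and data collection are unchanged.

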#### 5.2 Analysis population

All collected data from each participant will be analysed using a linear mixed effects model as specified in 6.1 Statistical methods. As this study aims to investigate the chronic and acute-on-chronic metabolic and cardiac effects of a novel lactate-ketone ester, certain modifications to the primary analysis may become necessary in a “modified Intention-to-Treat” approach. For instance, if a participant is unable to complete both study periods for reasons justified in the 4.2 Study dropout section their data will not be included in the final analysis.

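### The last-resort analysis dichotomises at an unstated cut-off and applies McNemar's exact test; with 10 pairs no observed difference below 60 percentage points can be significant, and an exact rank test would be a better fallback

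*SAP*

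**What the plan says.** SAP section 6.1 sets out three steps. A linear mixed model is fitted first. If residual plots show violations, the outcome is log-transformed. If neither model is usable, the data go to McNemar's exact test, "assuming that order and visit have no effect, with a contextual cut-off applied for classification".

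This paragraph follows both the single-time-point model, which covers the co-primary endpoints, and the repeated-measures model. For repeated measures, "pairwise between-treatment differences will be tested at each time point". Secondary endpoints are brought in too: "The analysis methods for the secondary endpoints will mirror those outlined for the primary outcomes".

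The number of pairs follows from three places:
- Section 3, for each co-primary endpoint: "Thus, 10 participants need to be enrolled".
- Section 4.2: "Participants who withdraw will be replaced to reach the target enrollment as specified in the power analysis".
- Section 5.2, on participants who do not complete both periods: "their data will not be included in the final analysis".

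The plan is therefore for 10 complete pairs. Section 5.1 sets two-sided P<0.05.

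**The concern.** The SAP writes the fallback rule itself but leaves its deciding input open. McNemar's test sees only which side of the cut-off each measurement falls on, so the cut-off largely determines the answer. Nothing says what it is or that it is fixed before unblinding.

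The method is also wasteful. A continuous or ordinal paired outcome becomes yes/no, and only discordant pairs count. With 10 pairs little information is left, and the effect can no longer be estimated on the outcome's own scale. An outcome sent down this route could show a large, consistent treatment difference and still be reported as non-significant.

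**Working it through.** **1. The plan's own sample size.** Section 3 gives, for insulin sensitivity, 0.30 × 3.0 = 0.9 with SD 0.9, and for cardiac output 0.25 × 5.6 = 1.4 with SD 1.4. Both standardised differences are 1.0. A two-sided paired t-test (noncentral t, noncentrality √n × 1.0) has power 0.748 at n = 9 and 0.803 at n = 10, so N = 10 reproduces. This takes the stated SD as the SD of within-participant differences. Since SD(diff) = SD × √(2(1−ρ)), that equals a between-participant SD with correlation ρ = 0.5. The SAP does not state ρ.

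**2. Which tables can be significant.** For discordant counts b and c, P = min(1, 2 × Pr[Bin(b+c, ½) ≤ min(b, c)]).

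| Split | P | Net difference, 10 pairs |
|---|---|---|
| 5-0 | 2/32 = 0.0625 | 50 points |
| 6-0 | 2/64 = 0.031 | 60 points |
| 7-1 | 2(1+8)/256 = 0.070 | 60 points |
| 8-1 | 2(1+9)/512 = 0.039 | 70 points |
| 8-2 | 2(1+10+45)/1024 = 0.109 | 60 points |
| 9-1 | 2(1+10)/1024 = 0.021 | 80 points |

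The splits 7-0 to 10-0 are also significant (P = 0.016 to 0.002). Every other split with at most 10 discordant pairs fails. The smallest significant observed difference is 60 points, and only if no pair goes the other way.

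**3. True difference needed for 80% power.** With no reverse pairs, power is Pr[Bin(10, δ) ≥ 6]: 0.633 at δ = 0.60, 0.794 at 0.67 and 0.813 at 0.68. So about 67 to 68 points are needed in this most favourable case.

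**4. Power at the planning effect.** Assume bivariate normal data, standardised difference 1.0 and ρ = 0.5. The discordant probabilities come from dichotomising both measurements at a common cut-off, and power is the exact trinomial sum over the tables in step 2.

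| Cut-off | Discordant probabilities | Power, n = 10 |
|---|---|---|
| Midway between the treatment means (best) | 0.419, 0.036 | 16% |
| At either treatment mean | 0.373, 0.031 | 10% |
| 1 SD from the midpoint | 0.262, 0.020 | 2% |

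About 24 pairs would be needed for 80% even at the best cut-off. The exact signed-rank test rejects when the smaller rank sum is at most 8 (P = 0.0488). Simulated on the same paired differences, its power is about 79%.

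The correlation is an assumption, so the range matters:

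| ρ | McNemar, best cut-off | Signed-rank |
|---|---|---|
| 0 | 18% | 50% |
| 0.3 | 17% | 64% |
| 0.5 | 16% | 79% |
| 0.7 | 15% | 94% |
| 0.8 | 14% | 99% |

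**5. Effect of leaving the cut-off open.** In the same normal setting, suppose the cut-off is whichever observed value gives the smallest P. The chance of significance rises from 16% to about 46% (43 to 47% for ρ from 0 to 0.8). With no treatment difference, the same search rejects in at most about 4% of trials.

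**6. Zero-heavy scores, the more likely users of this branch.** The SAP gives no score distribution. These simulations assume integer scores with many zeros and ρ = 0.5. Shapiro-Wilk P<0.05 on the residuals of both models stands in for visual inspection. Power is among trials reaching the branch; ranges cover a log constant of 0.1 or 1.

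| Zeros, placebo/active | Reach branch | McNemar, score above 0 (best) | McNemar, score above 1 | Signed-rank | Rank-sum |
|---|---|---|---|---|---|
| 74%/36% | 14–17% | 16–17% | 4–5% | 19–23% | 22–26% |
| 80%/50% | 34–39% | 4–5% | 1% | 6% | 7% |
| 60%/25% | 5–6% | 18–20% | 8–10% | 26–31% | 29–35% |
| 90%/30% | 25–26% | 68–75% | 31–37% | 71–79% | 72–80% |

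Rank-sum here compares within-participant period differences between sequences. With ρ from 0.3 to 0.7 also tried at 74%/36%, it gains 2 to 19 points over McNemar's best cut-off. The signed-rank test gains about 0 to 15.

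**The case against.** The best defence is that this is a last resort after two models, that the SAP declares its assumption about order and visit openly, and that cardiac output and clamp-derived insulin sensitivity are unlikely to reach it. That stands and limits the weight of the point.

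The rank test is no cure for a trial of 10. It too needs at least six non-zero differences: five in one direction give P = 0.0625. In three of the four zero-heavy settings its power is only 6 to 35%. That also stands, but it argues for modest expectations, not for dichotomising.

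A reader might infer more than the SAP supports:
- *That false positives are inflated.* With one pair per participant, McNemar's maximum size at n = 10 is 2.6% at a fixed cut-off, and the search in step 5 stayed under 5%. The harm shown is lost information and an arbitrary result.
- *That period adjustment is lost for the co-primary and other single-time-point outcomes.* The model replaced there has treatment, sequence and a participant intercept, but no period or visit term. With complete pairs its treatment estimate is already the mean paired difference. The "random intercepts for participant and for visits nested within participants" belong only to the repeated-measures model.
- *That several time points would be pooled as separate pairs.* Section 6.1 tests at each time point, so one McNemar test per time point is the natural reading.
- *That the beverage tolerability questionnaire will end up here.* Section 2.3 lists it as a secondary endpoint, so the rule covers it, but whether it fails both models is unknown.

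**Conclusion.** The point holds as a low-cost improvement to a conditional step. The 60-point floor rests only on the planned 10 complete pairs, two-sided P<0.05 and the conventional exact test; with 9 pairs it is 67 points and with 12 it is 50. The contrast of about 16% with about 79% rests on normal data, the planning effect and ρ = 0.5. It illustrates how much dichotomising discards and does not forecast data that fail both models. For such data the assumed zero-heavy settings show a smaller gain over the best cut-off and a larger one over a poor cut-off. In every setting the result depends on a choice that the SAP leaves open.

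**What to change.** Replace the McNemar sentence in section 6.1 with text to this effect:

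> Whether either mixed model is adequate is decided from the residual plots with treatment labels masked, before unblinding. If neither is adequate, treatments are compared by an exact (permutation, mid-rank) Wilcoxon signed-rank test of within-participant differences, with the Hodges-Lehmann estimate and 95% CI. For repeated measures the test is applied at each time point, with one pair per participant.

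If adjustment for period is wanted, an exact rank-sum test of period differences between sequences is an option. It costs power on near-normal data: about 68% against 79% in the step 4 setting with five participants per sequence.

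If a binary summary is kept, state its cut-off for each outcome before unblinding and report the paired difference in proportions with a 95% CI.

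The cost is a few SAP sentences and a short permutation routine in R. The main downside is that with many ties the Hodges-Lehmann estimate can be exactly 0. For the period-difference version this happened in 1 to 41% of branch-reaching trials across three of the zero-heavy settings. The distribution of within-participant differences should therefore be shown beside it.
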